12.2.2.2 Key secondary variables

The changes from baseline to Week 24 (LOCF) in FPG and total body weight will be analyzed and presented in similar way as the primary efficacy analysis described in Section [12.2.2.1](#).

12.2.2.3 Other secondary efficacy variables

The following variables, except for the percent changes from baseline in lipids and body weight, will be analysed based on similar ANCOVA model as the primary efficacy analysis described in Section [12.2.2.1](#). The percent changes from baseline to Week 24 (LOCF) in lipids (TC, LDL-C, HDL-C and fasting TG) and body weight will be analysed on a log scale in an ANCOVA model with terms similar to the primary efficacy analysis.

- the percent change from baseline in total body weight at Week 24 (LOCF)

- the change from baseline in seated SBP in subjects with baseline seated SBP ≥ 130 mmHg at Week 24 (LOCF)
- the change from baseline in total body weight in subjects with baseline BMI ≥ 25 kg/m² at Week 24 (LOCF)
- the change from baseline in HbA1c at Week 24 (LOCF) in subjects with baseline HbA1c $\geq 7.5\%$
- the change from baseline in seated SBP at Week 24 (LOCF)
- the change from baseline in waist circumference at Week 24 (LOCF)
- the percent change from baseline in fasting lipids (TC, LDL-C, HDL-C and TC) at Week 24 (LOCF)
- the change from baseline in fasting insulin and C-peptide at Week 24 (LOCF)
- the change from baseline in glicocalbumin at Week 24 (LOCF)

For the following proportions, estimates, confidence intervals, and tests will be obtained using the methodology of Zhang, Tsiatis and Davidian ([Zhang M et al 2007](#)) and Tsiatis, Davidian, Zhang and Lu ([Tsiatis A et al 2007](#)) with adjustment for gender and baseline variable (eg, adjustment for baseline HbA1c). For each treatment group, the probability of response is first modeled using a logistic regression model with gender and baseline (eg, baseline HbA1c) as the covariate. Treatment group estimates of response rate are then obtained by integrating each group's modeled probability of response over the observed distribution of baseline covariate (combined across groups). The difference in response rate between each of the dapagliflozin treatment groups and the placebo group will be displayed along with the 95% confidence intervals. Nominal p-values for the difference between the dapagliflozin treatment groups versus placebo will be provided (if applicable). When there are less than 5 responders on average by treatment group, the unadjusted (and difference) proportions, exact 95% confidence interval, and p-values from the Fisher's exact test (when applicable) will be provided.

- the proportion of subjects achieving a therapeutic glyceic response, defined as HbA1c $< 6.5\%$, at Week 24 (LOCF)
- the proportion of subjects achieving a therapeutic glyceic response, defined as HbA1c $< 7\%$ at Week 24 (LOCF) in subjects with baseline HbA1c $\geq 7\%$.
- the proportion of subjects discontinued for lack of efficacy or rescued for failing to maintain FPG below pre-specified rescue criteria at Week 12, 16, and 24 (LOCF)
- the proportion of subjects with baseline elevated BP (baseline SBP ≥ 130 mmHg and/or baseline DBP ≥ 80 mmHg) who achieve a seated BP of $< 130/80$ mmHg at Week 24 (LOCF)

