3.1.4 Double-blind Placebo-controlled Treatment Period (24 weeks)

Subjects randomized (1:1:1) to 1 of 3 treatment groups (dapagliflozin 5 mg, 10 mg and placebo).

Either gender needs to be 40% or higher of total number of randomised subjects. Also, the proportion of subjects with HbA1c $\geq 6.5\%$ but $\leq 7\%$ at Visit 5 needs to be at most approximately 25% of the total number of randomised subjects.

After the randomization visit, subjects will be followed up at Visit 7 (Week 1) and then at the subsequent visits at 4-week intervals between Visit 6 (Week 0) and Visit 13 (Week 24).

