Other secondary outcome variables and exploratory outcome variables shall provide supportive efficacy and safety information regarding the differences between the treatment groups. For other secondary efficacy variables, supportive statistical test will be made at nominal significance level 0.05 and nominal p-values will be reported.

Unless otherwise specified, for all changes (or percent changes) from baseline to a specific time point post-baseline as well as for glycemic therapeutic response definitions, analyses will be based on measurements available at that time point or the last post baseline measurement prior to the time-point, if no measurement is available at that time point, ie, last observation carried forward (LOCF). For rescued subjects, values collected after initiation of rescue medication will not be considered in calculating the LOCF values for glycemic endpoints.

The time course of all continuous variables will be presented using standard descriptive summary statistics.

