12.3 Determination of sample size

Each pairwise treatment group comparison will be tested at a significance level of approximately 0.027, according to Dunnett's method, in order to maintain an overall type I error rate < 0.050 for the primary objective. To detect a difference of 0.5% between each dapagliflozin group versus placebo for changes in HbA1c from baseline to Week 24, assuming a SD = 0.9%, and at a two-sided significance level of 0.027, 80 evaluable subjects are needed in each treatment group to provide 90% power. The assumed SD=0.9 is considered to be appropriate based on Japan Phase IIb study and Global monotherapy Phase III study result where SD was approximately 0.52% and 0.91%, respectively. Assuming that approximately 5% of the subjects will not have a post-baseline efficacy measurement, 85 subjects per treatment group (255 subjects total) are planned for randomization.

The sample size for this study was selected to be consistent with the research hypothesis as described in Section 1.2.

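### The switch to exact methods depends on an average responder count over the arms, while the logistic model is fitted arm by arm, so an arm with 0 or 1 responders can keep a model with no finite fit

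*Protocol*

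**What the plan says.** Protocol Section 12.2.2.3 sets one method for four binary endpoints: HbA1c below 6.5%, HbA1c below 7%, attainment of the blood pressure target, and "the proportion of subjects discontinued for lack of efficacy or rescued for failing to maintain FPG below pre-specified rescue criteria".

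- **Model.** "For each treatment group, the probability of response is first modeled using a logistic regression model with gender and baseline" as covariates. This is an intercept and two slopes in every arm.
- **Standardisation.** Response rates come from "integrating each group's modeled probability of response over the observed distribution of baseline covariate (combined across groups"). The difference from placebo is then shown with a 95% confidence interval.
- **Fallback.** "When there are less than 5 responders on average by treatment group, the unadjusted (and difference) proportions, exact 95% confidence interval" are to be used, and "p-values from the Fisher's exact test (when applicable) will be provided". No other condition leads to the exact methods.
- **Status.** Section 12.2.2 places these endpoints outside the testing hierarchy: "For other secondary efficacy variables, supportive statistical test will be made at nominal significance level 0.05".

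Section 3.1.4 gives three arms at 1:1:1. Section 12.3 plans 85 randomised and 80 evaluable subjects per arm. The protocol gives no expected response or rescue rate for any arm.

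**The concern.** A fallback for sparse data should act when the model cannot be fitted. Here the model is fitted within an arm, but sparsity is judged on a mean over arms. An effective treatment makes counts unequal: rescue could be common on placebo and almost absent on dapagliflozin. The many events in one arm then hold the average at 5 or more while another arm has almost none, and the plan, followed as written, calls for a logistic fit that does not exist in that arm.

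At stake are whether the arm's model can be estimated and, with no responders at all, the uncertainty attached to that arm. The primary and key secondary analyses are not touched.

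**Working it through.** **Arm size.** The plan's own figure reproduces: 2 × (2.2115 + 1.2816)² × 0.9² / 0.5² = 79.07, so 80 per arm, with power 0.904; 80 / 0.95 = 84.2, so 85. The plan has no figure for the binary endpoints other than the threshold of 5.

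**Trigger.** With three arms, an average below 5 means a total below 15.

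| Placebo / 5 mg / 10 mg | Average | Method |
|---|---|---|
| 12 / 0 / 0 | 4.0 | exact |
| 15 / 0 / 0 | 5.0 | per-arm logistic |
| 15 / 1 / 1 | 5.67 | per-arm logistic |

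**When the fit fails.** With 0 responders the intercept goes to minus infinity. With 1 responder, one gender has no events and the gender coefficient diverges. Both are certain. With k responders, a simple cause of failure is that all share one gender. At a 50:50 split the chance is about 2 × 0.5^k. At 40:60, the limit that Section 3.1.4 allows for the whole trial, it is 0.4^k + 0.6^k. The simulation checked separation by linear programming (80 subjects, 50:50 gender, 600 arms per count, three assumed baseline slopes) and also counts separation that involves baseline.

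| Responders in arm | Gender only, 50:50 | Gender only, 40:60 | Simulated |
|---|---|---|---|
| 0 or 1 | certain | certain | 100% |
| 2 | 50% | 52% | 49–60% |
| 3 | 25% | 28% | 20–30% |
| 4 | 12.5% | 15.5% | 12–13% |
| 5 | 6.3% | 8.8% | 6–9% |

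**How often the rule misses such an arm.** The rates are assumptions. Exact binomial probabilities, 85 per arm, total of at least 15:

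| Placebo | Dapagliflozin 5 mg / 10 mg | Model kept | Model kept and some arm has 0–1 |
|---|---|---|---|
| 10% | 1% / 1% | 8% | 7.2% |
| 10% | 1% / 2% | 14% | 10.2% |
| 10% | 2% / 2% | 21% | 10.5% |
| 15% | 1% / 1% | 48% | 45% |
| 15% | 2% / 2% | 66% | 44% |
| 20% | 1% / 1% | 86% | 82% |
| 20% | 2% / 2% | 93% | 67% |
| 25% | 1% / 1% | 98% | 94% |
| 25% | 2% / 2% | 99% | 73% |

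At placebo 5% the model is kept in about 1% of trials or fewer.

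**Effect on intervals.** For 0/85 the fitted risk tends to 0 and a model-based interval for the arm is about 0 to 0. The exact upper limit is 1 − 0.025^(1/85) = 4.2%.

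For the difference, simulation used the per-arm standardised estimator with an influence-function standard error: 80 per arm, 3,000 trials per scenario, one arm at 1–3% and the other at 15–20%. Only trials with an average of at least 5 were kept.

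- A compared arm had 4 or fewer responders in 88–100% of the trials kept. Coverage in those was 0.94–0.97.
- Where a compared arm had 0 responders, coverage was 0.85–0.95, because that arm adds no variance.
- Lower values arose in small selected fractions: 0.855 at 10% v 30% (the 8% of trials with a compared arm at 4 or fewer), and 0.775 at 20% v 2% with 40 per arm (the 4% of trials kept).

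For 15/80 v 0/80, the unadjusted Wald interval is −0.273 to −0.102 and the Newcombe interval is −0.287 to −0.103. The practical difference is small.

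**The case against.** The case for leaving the rule alone has force on several points.

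- **Not every sparse arm fails.** A reader might infer that any arm with 0 to 4 responders is unestimable. Failure is certain only at 0 and 1; at 3 and 4 most fits exist. Even under separation the fitted probabilities converge, so a standardised rate can still be computed.
- **The displayed interval mostly holds.** A reader might infer that the interval for the contrast is wrong. The interval that Section 12.2.2.3 says will be displayed is for the difference, and its coverage was mostly near nominal. The 0.85–0.95 is also conditional on having observed a zero, and nominal coverage does not promise 95% within such a selection.
- **The rates are assumed.** Section 4.2 excludes FPG above 240 mg/dL before randomisation, and Section 3.1.4.1 allows rescue only from Week 12 after two values above 200 mg/dL. Placebo rescue may be rare, and the average rule then usually fires. For HbA1c below 6.5%, up to about 25% of subjects may enter at 6.5–7%. With that stratum full, SD 0.9 and little mean change, placebo response is about 11–17%, and fewer than 5 placebo responders occur in 0–5% of trials. A smaller low stratum or a smaller SD raises that chance.
- **The wording is ambiguous.** The phrase could be meant arm by arm, in which case the words on averaging are the slip.
- **The SAP.** A reader might infer that a substitute method would be picked after unblinding. The protocol does not support this: Section 12 promises a comprehensive SAP before clean file, and handling of non-convergence may properly sit there.

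These points limit the size of the problem but do not remove it. The threshold is a rule the protocol states, and on its likelier reading it leaves 15/0/0 with a model that cannot be fitted.

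**Conclusion.** The mismatch is real and its consequences are modest. On the natural reading of the trigger, an arm with 0 or 1 responders can stay with a logistic model that has no finite maximum-likelihood fit. With 85 per arm and 1–2% in each dapagliflozin arm, this happens in about 44–94% of trials if the placebo rate is 15–25%, in about 7–10.5% if it is 10%, and hardly ever at 5%. All these rates are assumptions. The main statistical harm is with a zero-responder arm: no variance for that arm, and coverage of the difference of about 0.85–0.95 in simulation. Severity is low, because the endpoints are supportive with nominal p-values and no primary or key secondary conclusion depends on them.

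**What to change.** In Section 12.2.2.3, replace the averaged trigger with: *fewer than 5 responders, or fewer than 5 non-responders, in either treatment group of the comparison*. Then use the unadjusted proportions, exact 95% interval and Fisher's exact test already named. Apply the same fallback if a per-arm fit does not converge, because 6–9% of simulated arms with 5 responders were still separated. Carry the wording into the SAP.

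The cost is one sentence and some loss of precision, since the unadjusted exact analysis would be used more often. Under the 80-per-arm scenarios above, 88–100% of the trials that now keep the model would switch for that comparison. The two doses may then be compared with placebo by different methods, which the tables should label.

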12.2.3 Safety analysis

The safety evaluations will include analyses of AEs, laboratory parameters, ECG, vital signs (pulse and BP), hypoglycemic events, eGFR and physical examination.

The analysis of safety will be based on the safety analysis set. Safety data gained during the 24-week double-blind treatment period and the 3-week safety follow-up period will be evaluated. Safety variables will be summarized descriptively and missing data will be replaced using the LOCF approach where appropriate. Information about adjudicated cardiovascular events will be combined with the results from other dapagliflozin Phase II and Phase III studies to monitor cardiovascular safety. Results of analyses will be reported elsewhere.

12.3 Determination of sample size

Each pairwise treatment group comparison will be tested at a significance level of approximately 0.027, according to Dunnett's method, in order to maintain an overall type I error rate < 0.050 for the primary objective. To detect a difference of 0.5% between each dapagliflozin group versus placebo for changes in HbA1c from baseline to Week 24, assuming a SD = 0.9%, and at a two-sided significance level of 0.027, 80 evaluable subjects are needed in each treatment group to provide 90% power. The assumed SD=0.9 is considered to be appropriate based on Japan Phase IIb study and Global monotherapy Phase III study result where SD was approximately 0.52% and 0.91%, respectively. Assuming that approximately 5% of the subjects will not have a post-baseline efficacy measurement, 85 subjects per treatment group (255 subjects total) are planned for randomization.

The sample size for this study was selected to be consistent with the research hypothesis as described in Section 1.2.

12.4 Data monitoring committee – Not applicable

13. IMPORTANT MEDICAL PROCEDURES TO BE FOLLOWED BY THE INVESTIGATOR

13.1 Medical emergencies and AstraZeneca contacts

The Principal Investigator is responsible for ensuring that procedures and expertise are available to handle medical emergencies during the study. **A medical emergency usually constitutes an SAE and is to be reported as such, see Section 6.4.4**

In the case of a medical emergency the investigator may contact the Study Delivery Team Leader. If the Study Delivery Team Leader is not available, contact the Study Delivery Team Physician.

Name	Role in the study	Address & telephone number
	Study Delivery Team Leader	
	Study Delivery Team Physician	
Monitor	Study Delivery Team Monitor	See Supplement A, “Investigators and Study Administrative Structure”.

13.2 Overdose

Overdose is defined as the accidental or intentional ingestion of any dose of investigational product that is considered both excessive and medically important. Dapagliflozin has been well tolerated at doses of up to 500 mg/day in single dose testing in healthy volunteers and up to 100 mg/day in repeat dose testing for 14 days in healthy volunteers and subjects with T2DM. Once an investigator decides that a particular occurrence is an overdose, it must be reported as a SAE. If an overdose is suspected, monitoring of vital functions as well as treatment as appropriate should be performed.

13.3 Pregnancy

All outcomes of pregnancy must be reported to AstraZeneca.

Pregnancy itself is not regarded as an adverse event unless there is a suspicion that the investigational product under study and/or metformin and/or glymeperide may have interfered with the effectiveness of a contraceptive medication. Congenital abnormalities/birth defects and spontaneous miscarriages should be reported and handled as SAEs. Elective abortions without complications should not be handled as AEs. The outcome of all pregnancies (spontaneous miscarriage, elective termination, normal birth or congenital abnormality) must be followed up and documented even if the subject was discontinued from the study.

If any pregnancy occurs in the course of the study, the subject should be discontinued, the investigational product should be stopped and then investigators or other site personnel must inform appropriate AstraZeneca representatives immediately but no later than the end of the next business day of when he or she becomes aware of it.

The PREGREP module in the eCRF is used to report the pregnancy. This module in the eCRF should be completed by the investigator and the AstraZeneca representative will forward the information to Bristol Myers Squibb using the same procedure as for SAE reporting. An

AstraZeneca paper Pregnancy Outcome Report, part 2, is used to report the outcome of the pregnancy.

Appendix B
Additional Safety Information

FURTHER GUIDANCE ON THE DEFINITION OF A SERIOUS ADVERSE EVENT (SAE)

Life threatening

‘Life-threatening’ means that the subject was at immediate risk of death from the AE as it occurred or it is suspected that use or continued use of the product would result in the subject’s death. ‘Life-threatening’ does not mean that had an AE occurred in a more severe form it might have caused death (eg, hepatitis that resolved without hepatic failure).

Hospitalisation

Outpatient treatment in an emergency room is not in itself a serious AE, although the reasons for it may be (eg, bronchospasm, laryngeal oedema). Hospital admissions and/or surgical operations planned before or during a study are not considered AEs if the illness or disease existed before the subject was enrolled in the study, provided that it did not deteriorate in an unexpected way during the study.

Important medical event or medical intervention

Medical and scientific judgement should be exercised in deciding whether a case is serious in situations where important medical events may not be immediately life threatening or result in death, hospitalisation, disability or incapacity but may jeopardize the subject or may require medical intervention to prevent one or more outcomes listed in the definition of serious. These should usually be considered as serious.

Simply stopping the suspect drug does not mean that it is an important medical event; medical judgement must be used.

Examples of such events are:

- Angioedema not severe enough to require intubation but requiring iv hydrocortisone treatment
- Hepatotoxicity caused by paracetamol (acetaminophen) overdose requiring treatment with N-acetylcysteine
- Intensive treatment in an emergency room or at home for allergic bronchospasm
- Blood dyscrasias (eg, neutropenia or anaemia requiring blood transfusion, etc) or convulsions that do not result in hospitalisation
- Development of drug dependency or drug abuse

A GUIDE TO INTERPRETING THE CAUSALITY QUESTION

The following factors should be considered when deciding if there is a “reasonable possibility” that an AE may have been caused by the drug.

- Time Course. Exposure to suspect drug. Has the subject actually received the suspect drug? Did the AE occur in a reasonable temporal relationship to the administration of the suspect drug?
- Consistency with known drug profile. Was the AE consistent with the previous knowledge of the suspect drug (pharmacology and toxicology) or drugs of the same pharmacological class? OR could the AE be anticipated from its pharmacological properties?
- Dechallenge experience. Did the AE resolve or improve on stopping or reducing the dose of the suspect drug?
- No alternative cause. The AE cannot be reasonably explained by another aetiology such as the underlying disease, other drugs, other host or environmental factors.
- Rechallenge experience. Did the AE reoccur if the suspected drug was reintroduced after having been stopped? AstraZeneca would not normally recommend or support a rechallenge.
- Laboratory tests. A specific laboratory investigation (if performed) has confirmed the relationship?

A “reasonable possibility” could be considered to exist for an AE where one or more of these factors exist.

In contrast, there would not be a “reasonable possibility” of causality if none of the above criteria apply or where there is evidence of exposure and a reasonable time course but any dechallenge (if performed) is negative or ambiguous or there is another more likely cause of the AE.

In difficult cases, other factors could be considered such as:

- Is this a recognised feature of overdose of the drug?
- Is there a known mechanism?

Ambiguous cases should be considered as being a “reasonable possibility” of a causal relationship unless further evidence becomes available to refute this. Causal relationship in cases where the disease under study has deteriorated due to lack of effect should be classified as no reasonable possibility.

Clinical Study Protocol Appendix C

Drug Substance	Dapagliflozin
Study Code	D1692C00006
Edition Number	1
Date	

**Appendix C
International Airline Transportation Association (IATA) 6.2 Guidance
Document**

LABELLING AND SHIPMENT OF BIOHAZARD SAMPLES

International Airline Transportation Association (IATA) classifies biohazardous agents into 3 categories (http://www.iata.org/whatwedo/cargo/dangerous_goods/infectious_substances.htm). For transport purposes the classification of infectious substances according to risk groups was removed from the Dangerous Goods Regulations (DGR) in the 46th edition (2005). Infectious substances are now classified either as Category A, Category B or Exempt. There is no direct relationship between Risk Groups and categories A and B.

Category A Infectious Substances are infectious substances in a form that, when exposure to it occurs, is capable of causing permanent disability, life-threatening or fatal disease in otherwise healthy humans or animals. Category A pathogens are eg, Ebola, Lassa fever virus:

- are to be packed and shipped in accordance with IATA Instruction 602.

Category B Infectious Substances are infectious Substances that do not meet the criteria for inclusion in Category A. Category B pathogens are eg, Hepatitis A, B, C, D, and E viruses, Human immunodeficiency virus (HIV) types 1 and 2. They are assigned the following UN number and proper shipping name:

- UN 3373 – Biological Substance, Category B
- are to be packed in accordance with UN3373 and IATA 650

Exempt - all other materials with minimal risk of containing pathogens

- Clinical trial samples will fall into Category B or exempt under IATA regulations
- Clinical trial samples will routinely be packed and transported at ambient temperature in IATA 650 compliant packaging (http://www.iata.org/whatwedo/cargo/dangerous_goods/infectious_substances.htm)
- **Biological samples transported in dry ice require additional dangerous goods specification for the dry-ice content**
- IATA compliant courier and packaging materials should be used for packing and transportation and packing should be done by an IATA certified person, as applicable

- Samples routinely transported by road or rail are subject to local regulations which require that they are also packed and transported in a safe and appropriate way to contain any risk of infection or contamination by using approved couriers and packaging / containment materials at all times. The IATA 650 biological sample containment standards are encouraged wherever possible when road or rail transport is used.

Clinical Study Protocol Appendix D

Drug Substance	Dapagliflozin
Study Code	D1692C00006
Edition Number	1
Date	

